4.2 Interim Analysis

No formal interim analysis is planned for this study.

5 CHANGES IN THE PLANNED ANALYSES

The following major changes to the statistical methods in this analysis plan were made after Amendment 03 of the Protocol was approved.

- Additional time points (ie., Months 2, 4, 5) have been included in MMRM as covariates for the primary and key secondary analysis.
- An additional safety analysis set (ie., On-Treatment Safety Analysis Set) has been defined and the safety analysis based on the On-Treatment Safety Analysis Set has been added.

The full changes to the statistical methods in this analysis plan were made in version 2.0 of the SAP from version 1.0 are detailed in [Table 1](#) at the beginning of the SAP.

6 DEFINITIONS AND CONVENTIONS FOR DATA HANDLING

6.1 Efficacy Data Handling

6.1.1 Baseline Efficacy

For the analyses of PBO-controlled endpoints (ie, Day 1 to Month 6), “Study Baseline” is defined as the data captured during the Run-In Period (or during the Baseline Period). For the analyses of data that are not placebo-controlled (ie, Month 7 to Month 12), data from the Month 6 visit will be used as the “Period 2 Baseline” for some analyses.

Unless otherwise specified, the Study Baseline measurement is the last observed measurement among all available measurements, including from unscheduled assessments, prior to the first dose of randomized study medication for a given assessment. For the following endpoints, baseline measurement is defined as follows:

- Sleep diary parameters: the mean of diary data entered on the last 7 mornings before Visit 3a during the Run-In Period
- ISI: Last available ISI measurement on or before Visit 3a (excluding Visit 1)
- FSS: Last available FSS measurement on or before Visit 3a (excluding Visit 1)
- EQ-5D-3L: Last available EQ-5D-3L measurement on or before Visit 3a (excluding Visit 1)
- WPAI-GH: Last available WPAI-GH measurement on or before Visit 3a (excluding Visit 1)

For each Sleep Diary parameter at baseline, if no more than 2 of the final 7 nights’ values are missing, the available values will be used to calculate the mean. If more than 2 values are missing, the parameter will be considered missing for baseline. For each Sleep Diary parameter during the treatment period and follow-up period, if at least 4 of the 7 nights’ values are available, the available values will be used to calculate the mean. If fewer than 4 values are available, the parameter will be considered missing for the corresponding time point.

For the analysis using the MMRM assuming MAR (no missing value imputation), the above handling will be used to obtain the average of weekly (7 days) diary parameter values.

6.1.2 Derivation of Primary and Key Secondary Endpoints for Sleep Diary

Each Sleep Diary parameter will be derived by calculating the average of weekly (7 days) diary parameter values.

Baseline is the mean of diary data entered on the last 7 mornings during the Run-In Period before randomization; sleep diary parameter of the first 7 nights is the mean of diary data entered on the first 7 mornings following the start of treatment; sleep diary parameter for each visit is the mean of diary data entered on the last 7 mornings prior to that visit.

For the follow-up period, if the first 7 nights overlap with the last 7 nights (eg, the follow-up period is less than 14 days in total), the last non-overlap nights will be used in calculating the average value for the last 7 nights.

The following 7 questions are captured in the electronic Sleep Diary:

- Q1: What time did you try to go to sleep?
- Q2: How long did it take you to fall asleep?
- Q3: How many times did you wake up, not counting your final awakening?
- Q4: In total, how long did these awakenings last?
- Q5: What time was your final awakening?
- Q6: After your last awakening, how much longer did you try to sleep?
- Q7: What time did you get out of bed for the day?

The efficacy endpoints from electronic Sleep Diary are defined as follows:

- $sSOL = Q2$
- $sWASO = Q4 + (Q7 - Q5)$
- $sTST = TIB - \text{time spent awake}$ [where $TIB = Q7 - Q1$; and $\text{time spent awake} = Q2 + Q4 + Q7 - Q5$]
- $sSE = sTST/TIB$ (as defined above)

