9.1.2.4 End of Study Visit

At least 14 days but no more than 18 days after the Treatment Period, subjects will return to the clinic for the End of Study Visit.

At the End of Study Visit, in addition to standard safety assessments and the eC-SSRS, a urine drug test will be conducted, the Tyrer Benzodiazepine Withdrawal Symptom Questionnaire (T-BWSQ) will be administered and sleep diaries will be collected (Table 3). After the End of Study Visit, subjects' participation in the study will be finished.

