3.1.2 Secondary Endpoints

The key secondary endpoints are:

- Mean change from Study Baseline in sSE at Month 6

- Mean change from Study Baseline of sWASO at Month 6

Additional secondary endpoints are:

- Mean change from Study Baseline of sSOL, of sSE, of sWASO and of sTST, at the beginning of treatment (mean of the 7 nights after the 1st dose in Period 1), at Month 1 and at Month 3
- Mean change from Study Baseline of sTST at Month 6
- Proportion of responders at Month 6 and Month 12, where sleep onset responder is defined as follows: sSOL at Study Baseline is ≥ 30 minutes and mean sSOL at 6 months is ≤ 20 minutes, and sleep maintenance responder is defined as follows: sWASO at Study Baseline is ≥ 60 minutes and mean sWASO at 6 months is ≤ 60 minutes and shows a reduction of >10 minutes compared to Study Baseline.
- Change from Study Baseline in daytime functioning, assessed as the total score from the 4 items on daytime functioning, on the ISI, at Months 1, 3, and 6
- Change from Study Baseline on the FSS at Months 1, 3, and 6
- Ratings on the morning sleepiness item of the Sleep Diary, for:
 - The mean change from Study Baseline of the 1st 7 mornings after the 1st dose in Period 1 and Period 2
 - The mean change from Study Baseline at: Month 1, Month 3, and Month 6
 - The mean change from Study Baseline and from Treatment Period 2 Baseline (as appropriate): for subjects with 1, 3, 6, 9 and 12 months exposure
 - The mean change from Screening for the 1st 7 mornings and 2nd 7 mornings of the Follow-up Period
- Rebound insomnia endpoints as assessed from the Sleep Diary during the Follow-up Period
 - Change from Screening of sSOL on each of the 1st 3 nights, mean sSOL of the 1st 7 nights, and mean sSOL of the 2nd 7 nights of the Follow-up Period
 - Change from Screening of sWASO on each of the 1st 3 nights, mean sWASO of the 1st 7 nights and mean sWASO of the 2nd 7 nights of the Follow-up Period
 - Proportion of subjects whose sSOL is longer than at Screening for each of the 1st 3 nights, or whose mean sSOL is longer than at Screening for 1st 7 nights or 2nd 7 nights of the Follow-up Period
 - Proportion of subjects whose sWASO is higher than at Screening for each of the 1st 3 nights, or whose mean sWASO is higher than at Study Baseline for the 1st 7 nights or 2nd 7 nights of the Follow-up Period
- Persistence of Effect
 - Mean change from Study Baseline of sSOL, of sSE, of sWASO and of sTST at Months 3, 6, 9, and 12 compared to Month 1

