 - The sleep onset responder is defined as: sSOL at Study Baseline (or Period 2 Baseline) is >30 minutes and mean sSOL at each month (Months 7, 8, 9, 10, 11 and 12) is ≤ 20 minutes,
 - The sleep maintenance responder is defined as: sWASO at Study Baseline (or Period 2 Baseline) is >60 minutes and mean sWASO at each month (Months 7, 8, 9, 10, 11

and 12) is ≤ 60 minutes and shows a reduction of >10 minutes compared to Study Baseline (or Period 2 Baseline).

The proportion of responders will be analyzed based on the subjects with sSOL > 30 minutes at the baseline for sSOL and separately the subjects with sWASO > 60 minutes at the baseline for sWASO.

- Morning sleepiness item of the Sleep Diary:
 - Change from Study Baseline of mean rating on morning sleepiness at the 1st 7 mornings after the 1st dose in Treatment Period 1, Month 1, Month 2, Month 3, Month 4, Month 5 and Month 6.
 - Change of mean rating on morning sleepiness from Study Baseline / Treatment Period 2 Baseline for 1st 7 mornings after the 1st LEM dose, 1, 3, 6, 9 and 12 months of exposure to LEM5 and LEM10. Data from subjects randomized to LEM5 or LEM10 at the start of the study will use Study Baseline, data from subjects who were re-randomized to LEM5 or LEM10 in Period 2 will use Treatment Period 2 Baseline. Change from Screening of mean rating on morning sleepiness of 1st 7 mornings and 2nd 7 mornings in Follow-Up Period.
- Rebound insomnia endpoints during the Follow-up Period as follows:
 - Change from Screening of sSOL on each of the 1st 3 nights, mean sSOL of the 1st 3 nights, mean sSOL of the 1st 7 nights, and mean sSOL of the 2nd 7 nights of the Follow-up Period
 - Change from Screening of sWASO on each of the 1st 3 nights, mean sWASO of the 1st 3 nights, mean sWASO of the 1st 7 nights and mean sWASO of the 2nd 7 nights of the Follow-up Period
 - Proportion of subjects whose sSOL is longer than at Screening by at least 5 minutes for each of the 1st 3 nights, mean sSOL of the 1st 3 nights, mean of the 1st 7 nights, and mean of the 2nd 7 nights of the Follow-up Period
 - Proportion of subjects whose sWASO is higher than at Screening by at least 5 minutes for each of the 1st 3 nights, mean sWASO of the 1st 3 nights, mean of the 1st 7 nights, and mean of the 2nd 7 nights of the Follow-up Period.

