The actual value of sSOL and sWASO will be analyzed separately using analysis of covariance model (ANCOVA) with factors of age group (<65 , and ≥ 65 years older), region (North America, Europe and New Zealand, Asia), and treatment for each time point (baseline, each of the first 3 nights, mean of the first 3 nights, mean of the first 7 nights, and mean of the last 7 nights of the Follow-up Period). The 95% CI of the treatment difference will be constructed for each time point. It will be considered as strong evidence of rebound insomnia if the lower bound of the 95% CI of sSOL or sWASO for each of the 3 nights, the mean of the first 3 nights, mean of the first 7 nights, and mean of the second 7 nights of the Follow-up Period exceeds the upper bound of a 95% CI for the values during the Screening Period in the given treatment group. If the LS means for sSOL and sWASO for the Follow-up Period are all lower than for the Screening Period, then no rebound insomnia is suggested. In this analysis, the treatment groups will be defined as the last randomized study treatment just before the Follow-up period.

- Analyses for persistence versus loss of effect will be conducted for sSOL, sSE, sWASO and sTST at Months 2 through Month 12 compared to Month 1.

The 95% CI for the change from Study Baseline of sSOL, sSE, sWASO and sTST at each visit will be calculated using the MMRM model assuming MAR (no missing value imputation) with factors of age group (<65, and ≥65 years older), region (North America, Europe and New Zealand, Asia), treatment, visit and treatment-by-visit interaction as fixed effect, and baseline value as covariate based on FAS. At each month beyond Month 1, the change from Study Baseline will be compared to either the lower bound of the 95% CI (for sSE and sTST) or the upper bound of the 95% CI (for sSOL and sWASO) at Month 1. Persistence of effect will be defined as present if the mean change from Study Baseline at Month 6 is above the lower bound of the 95% CI at Month 1 for sSE or sTST and below the upper bound of the 95% CI at Month 1 for sSOL and sWASO.

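### The SAP defines the second Follow-up week of the rebound analysis in two ways, which agree at 14 nights but diverge for a Follow-up of 15 to 18 nights

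*SAP*

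**What the plan says.** **Second seven nights.** SAP 3.1.2 lists "mean sSOL of the 1st 7 nights, and mean sSOL of the 2nd 7 nights of the Follow-up Period" among the rebound endpoints, and protocol 9.7.1.1.2 does the same for sSOL and sWASO. The rebounder proportions in SAP 3.4.2.4 use "mean of the 1st 7 nights, and mean of the 2nd 7 nights of the Follow-up Period". The decision rule in that section, which compares Follow-up confidence limits with Screening, also refers to the second seven nights.

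**Last seven nights.** The ANCOVA in SAP 3.4.2.4, in the same paragraph as the decision rule, is fitted at time points that end with "mean of the first 7 nights, and mean of the last 7 nights of the Follow-up Period". SAP 6.1.2 covers the case "if the first 7 nights overlap with the last 7 nights (eg, the follow-up period is less than 14 days in total" and says that then "the last non-overlap nights will be used in calculating the average value for the last 7 nights". Its general rule for visits also counts backwards: "sleep diary parameter for each visit is the mean of diary data entered on the last 7 mornings prior to that visit".

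**Timing.** Protocol 9.1.2.3 keeps the diary going each morning until the End of Study visit. Protocol 9.1.2.4 places that visit "At least 14 days but no more than 18 days after the Treatment Period", while footnote d of protocol Table 3 allows seven days either side of schedule. SAP Table 9, which sets the diary windows, stops at Month 12 and has no Follow-up rows.

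**The concern.** A single week-2 value cannot be both nights 8–14 and the final seven nights before a visit whose date varies. As written, the ANCOVA would be fitted to one window and the decision rule in the same paragraph would judge another. Under the second definition, the time since the last dose differs between subjects according to when they attended.

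Rebound is defined by what happens after the drug is stopped, so time since the last dose is part of the endpoint. The week-2 mean enters both the criterion for strong evidence of rebound and the criterion for no rebound. If 6.1.2 governs every derived week-2 value, it also feeds the week-2 rebounder proportion, which has a 5-minute threshold, and the week-2 morning sleepiness summary.

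**Working it through.** **Inputs.** Endpoint window: nights 8–14 (SAP 3.1.2). Modelled window: last seven nights (SAP 3.4.2.4 and 6.1.2). End of Study: day 14 to 18 (protocol 9.1.2.4), or within 7 days of schedule (Table 3, footnote d). SAP target days: 364 for Month 12 (Table 9) and 378 for End of Study (Table 10). Minimum data: 4 of 7 nights (SAP 6.1.1). Let F be the number of Follow-up nights. I take a visit on day F to give F nights, which is an assumption.

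**Step 1: reproduce the SAP's boundary.** The first seven nights are 1 to 7 and the last seven are F−6 to F. They overlap when F−6 ≤ 7, that is F ≤ 13, which is the under-14-day condition in 6.1.2. The targets give 378 − 364 = 14, where the last seven nights are 8–14 and the two definitions agree.

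**Step 2: which way the window is counted.** Nights 8–14 can never overlap nights 1–7. An overlap condition therefore makes sense only for a window counted back from the end of Follow-up.

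**Step 3: shared nights.** For F from 14 to 21, the last seven nights share 14 − (F−6) + 1 = 21 − F nights with nights 8–14.

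| F | Last seven nights | Shared with 8–14 |
|---|---|---|
| 14 | 8–14 | 7 |
| 15 | 9–15 | 6 |
| 16 | 10–16 | 5 |
| 17 | 11–17 | 4 |
| 18 | 12–18 | 3 |
| 21 (footnote d limit) | 15–21 | 0 |

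**Step 4: short Follow-up.** For F below 14 the overlap rule leaves nights 8 to F, which is F − 7 nights. A fixed 8–14 window holds the same nights. At F = 10 both have 3 nights and are missing under the 4-of-7 rule; at F = 11 both have 4 and are kept.

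**Step 5: possible size.** The documents give no fade rate, so this step is an assumption throughout. Suppose the excess over Screening halves every h nights. Each night in the last-seven window is F − 14 nights later than its counterpart in 8–14, so the ratio of the two means is 2^(−(F−14)/h).

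| Assumed h (nights) | Ratio at F = 15 | Ratio at F = 18 |
|---|---|---|
| 3 | 0.79 | 0.40 |
| 5 | 0.87 | 0.57 |
| 7 | 0.91 | 0.67 |
| 14 | 0.95 | 0.82 |
| no fade | 1.00 | 1.00 |

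As an illustration, take an assumed 20-minute excess on night 1 and h = 5. Nights 8–14 then average 5.2 minutes, and the last seven nights average 4.5 minutes at F = 15 and 3.0 at F = 18. The subject crosses the 5-minute threshold because of the visit date alone. The same curve averages 13.7 minutes over nights 1–7, so this subject is still counted as a rebounder in week 1.

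**The case against.** The strongest reply is that this is loose drafting. Follow-up is described as two weeks, the target is exactly 14 nights, and most of the text says second seven nights; protocol 9.7.1.6.2 speaks of each of the two weeks. The ANCOVA paragraph uses the two terms as if they were interchangeable, and no sentence in 6.1.2 expressly derives a week-2 value for a Follow-up longer than 14 nights. That stands in part: the end-counted reading for longer Follow-up is an inference from the overlap condition and the visit rule. But protocol 9.1.2.4 permits more than 14 nights, the diary runs throughout, and nothing caps the window at night 14.

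Four stronger readings are tempting, and the documents do not support them:

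- A reader might infer that the quoted overlap sentence itself moves the window. It applies only when Follow-up is under 14 nights, where it selects the same nights as the endpoint. It matters as evidence of how the window is counted.
- A reader might infer that the overlap rule loses data in short Follow-up. Step 4 shows the same missing values under a fixed window.
- A reader might infer a bias towards finding no rebound. That needs a rebound still fading after night 8, and the documents give no fade rate; the protocol reports no evidence of rebound in Study 201. The SAP also suggests no rebound only if all Follow-up means are below Screening, and an early rebound would still show in the unaffected early values.
- A reader might take four of the five days from 14 to 18 as a frequency. No distribution of visit dates is given, and footnote d sets a different range.

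**Conclusion.** The inconsistency is real and is more than clerical: it can change the computed week-2 value for any subject with more than 14 Follow-up nights. Within the 14-to-18-day window, the modelled week moves 1 to 4 nights later than the endpoint; at the footnote d limit it would move 7. These counts rest only on the end-counted reading and on one diary night per Follow-up day. The effect on the rebound estimate cannot be sized from the documents, and its sign depends on the time course of any excess.

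The reach is limited. The issue concerns the second-week values of additional secondary endpoints, which carry no multiplicity control. The primary and key secondary analyses are not affected.

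**What to change.** In SAP 6.1.2 and in the ANCOVA time-point list of 3.4.2.4, replace the last-seven-night wording with the second seven nights, defined as Follow-up nights 8–14 after the last dose. Keep the 4-of-7 rule for that window. Add rows for both Follow-up weeks to SAP Table 9. Drop the overlap sentence in 6.1.2, which becomes redundant; dropping it does not change missingness for short Follow-up. Reconcile the End of Study windows in protocol 9.1.2.4 and Table 3 footnote d.

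The cost is SAP wording, a consistency correction in the protocol and one programming window, with no new data. The downside is that diary nights after night 14 are not used in this endpoint.

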6.1.3 Visit Windowing

For the Sleep Diary, the following visit windowing rule in [Table 9](#) will be applied based on measurements from unscheduled visits and early termination visits to attain the measurement for analysis for the given scheduled visit.

Table 9 Windowing Rules for Efficacy Endpoints from Sleep Diary

Visit	Target Visit Day (in study days)	Visit Window (in study days)
First 7 nights	2	2 - 8
Visit 4 (Month 1)	30	24 - 30
Visit 5 (Month 2)	60	54 - 60
Visit 6 (Month 3)	90	84 - 90
Visit 7 (Month 4)	120	114 - 120
Visit 8 (Month 5)	150	144 - 150
Visit 9 (Month 6)	180	174 - 180 (or last 7 days prior to subject entering Period 2, whichever is earlier) *

Table 9 Windowing Rules for Efficacy Endpoints from Sleep Diary

Visit	Target Visit Day (in study days)	Visit Window (in study days)
Visit 10 (Month 7)	210	204 - 210
Visit 11 (Month 8)	240	234 - 240
Visit 12 (Month 9)	270	264 - 270
Visit 13 (Month 10)	300	294 - 300
Visit 14 (Month 11)	330	324 - 330
Visit 15 (Month 12)	364	Last 7 days from study days 358 - 371 (or last dose date + 1 for subjects who completed 12 months treatment, whichever is earlier)

*: If subjects discontinued the study and did not enter Treatment Period 2, last 7 days from study days 168 -180 will be used.

6.2 SAFETY DATA HANDLING

6.2.1 Baseline Safety

The baseline value for all safety endpoints will be the last non-missing measurement occurring prior to the first dose of the study medication.

For visit-based safety summaries there may be two different baseline value as followed:

- Study Baseline: defined as the last non-missing measurement occurring prior to the first dose of the study medication in Period 1.
- Treatment Period 2 Baseline: defined as the last non-missing measurement occurring prior to the first dose of the study medication in Period 2.

